#### *Mobile phone SMS (optional – for participants with a phone and who agree to optional SMS component):*

Participants who consent to SMS will receive weekly SMS sent in English, Kiswahili, or DhoLuo as part of a momentary ecological assessment of adherence and exposure. Exposure, i.e. have penatratve sex without a condom, will be referred to by a code word for added privacy: for example, "How many times did you dance this week?" If a participant is in the dPEP arm, they will receive a second SMS, "How many times did you take dPEP this week?" Encrypted transmission, password protection to open the surveys, and immediate deletion permit sensitive data to be collected safely.

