**Adherence:** All participants will receive 1:1 adherence counselling for PrEP with individualized barrier identification and problem-solving assistance. Participants in the dPEP arm will receive 1:1 adherence counselling as well as reminders on their daily PrEP tablet bottle as a reminder to assess personal need for dPEP on that day. A number of measures will be used to determine adherence:

**Self-reported measures:** Sexual behavior and, for those assigned to the dPEP arm, pill-taking behavior, will be measured by timeline follow-back calendar at each follow-up visit to assess exposures and dPEP use. Because dPEP is an exposure-driven medication, adherence is dependent on use of dPEP following each exposure.

**Real-time behavioral measurement (optional):** Weekly SMS will be sent in English, *KiSwahili* or *DhoLuo* as part of a momentary ecological assessment of adherence and exposure. Exposure (i.e., condomless sex) will be referred to by a code word for added privacy: for example, "How many times did you dance [have sex without a condom] this week?" [If in the dPEP arm] "How many times did you take dPEP this week?" We have used real-time SMS data collection in multiple prior PrEP studies in Kenya; cell phones are very common in Kenya (outnumbering citizens). Encrypted transmission, password protection to open the surveys, and immediate deletion permit sensitive data to be collected safely. Studies of PrEP demonstrated that there was improved comfort with reporting sexual behavior via SMS, though objective adherence measures were far superior to self-report.

**Objective measures:** Hair drug levels will be measured to more objectively assess quantitative exposures to dPEP, for several analyses. Hair samples (50-100 strands) will be collected following consent to collection and confirmed eligibility for hair collection (occipital hair >0.5cm in length with absence of bleaching) from all participants at each visit (Months 0/3/6/9/12). Hair samples will be shipped to [name] UCSF Hair Analytical Laboratory (HAL).

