### Secondary outcomes:

- Safety: Safety assessment will be measured in both arms: serious adverse events (SAEs), related all AEs and discontinuations (in the dPEP arm only), and a standardized symptom assessment for doxycycline-specific side effects (e.g., nausea, pill esophagitis, photosensitivity, vaginal candidiasis).
- Acceptability: Longitudinal change in qualitative themes and associated barriers and facilitators
- Adherence: We will explore the self-reported measures and SMS data, defining adherence as the percentage of times that dPEP was taken following an episode of condomless intercourse. Stored vaginal swabs for Y chromosome testing can be available for later validation.
- Resistance: The detection of the plasmid-encoded *tet(M)* gene and/or *tetR* genetic resistance determinants is indicative of phenotypic resistance to tetracycline
- Cost: The incremental cost effectiveness ratio (ICER) per incident STI case averted and DALY averted

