### **2.2.4. Adherence**

Adherence is only assessed in the dPEP arm

- Weekly SMS questions
  - Weekly questions collected in participants who opted in to SMS.
  - Number of days in the last 7 days when dPEP was taken
  - Number of days in the last 7 days when participants had sex or “danced”).
- Hair samples
  - Collected quarterly
    - Quantitative amount of doxycycline in 1cm segments from cut end to tip which corresponds with a 4-week period of dPEP use (starting 1 week ago).
- Self-report of coverage of sexual contacts in the prior 14 days to 3 days in the dPEP arm:
  - Quarterly (timeline follow-back) adherence questionnaire.

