## Measures

- Last 14 days (up to 3 days prior to visit) calendar reporting of days taking dPEP and days with sex.
- SMS: Self-reported coverage of last week: last 7 days # days with “dance” (SMS term used to mean sex), and # days taking dPEP.

Definition: Acceptable coverage for a participant is defined as on 80% of days with sex, the participant self-reports use of dPEP within 72 hours.

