## **9. ADDITIONAL SECONDARY ENDPOINT ANALYSIS**

### **9.1. Changes in sexual frequency**

SMS surveys collected weekly ask all participants how many days of the last week they had sexual intercourse with responses ranging from 0-7. We will compare frequency of sexual activity over time to investigate whether they differ by arm using a GEE with Poisson distribution.

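### The SAP's dPEP coverage rule counts every day with sex although dosing follows only condomless sex; separately, the protocol and SAP define the weekly SMS sex item differently

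*SAP*

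**What the plan says.** **Coverage.** Under Measures in SAP 8.5.1, acceptable coverage for a participant means that "on 80% of days with sex, the participant self-reports use of dPEP within 72 hours". The two sources are the calendar (days -14 to -3 before a visit) and the weekly SMS. Neither the definition nor the descriptive tables that follow it mention condoms. SAP 3.1 and 3.2 tie dosing to condomless sex. The protocol does the same for adherence, "defining adherence as the percentage of times that dPEP was taken following an episode of condomless intercourse" (10.0, Secondary outcomes; repeated in the adherence analysis paragraph).

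**SMS item.** The protocol's SMS subsection explains that exposure, to "have penatratve sex without a condom, will be referred to by a code word for added privacy". The Real-time behavioral measurement paragraph agrees: "Exposure (i.e., condomless sex) will be referred to by a code word for added privacy". Its sample text is "How many times did you dance [have sex without a condom] this week". The SAP describes the same item as "Number of days in the last 7 days when participants had sex" (2.2.4), glosses the code word as "SMS term used to mean sex" (8.5.1), and in 9.1 says the surveys "ask all participants how many days of the last week they had sexual intercourse", with replies from 0 to 7.

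**Condom data.** The protocol's sexual behavior questionnaire uses the timeline follow-back calendar to record sexual contacts with condom use over the past 3 months. SAP 9.1.1 analyses condom use from a separate quarterly question about last sex.

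**The concern.** dPEP is event-driven, so its adherence denominator should be the events that call for a dose. A rule that counts condom-protected days marks a woman as uncovered on days when she was not told to take anything. Among women who use condoms, coverage then mixes missed doses with protected sex. If efficacy proves weak, understated coverage would push the explanation towards non-use. The protocol also plans sensitivity analyses of cost-effectiveness for adherence and risk compensation.

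The SMS discrepancy matters for a second reason. The protocol's rationale names the assessment of disinhibition as one reason for an open-label design. A reader of 9.1 needs to know whether the weekly count is of sex or of sex without a condom, and whether the unit is acts or days.

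**Working it through.** The plan states no figure on this point, so there is none to reproduce. The check sets the definitions side by side and then sizes the denominator problem under stated assumptions.

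**1. Definitions**

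| Element | Protocol | SAP |
|---|---|---|
| When dPEP is taken | after condomless sex | after condomless sex (3.1, 3.2) |
| Adherence or coverage denominator | condomless episodes | all days with sex (8.5.1) |
| SMS code word | sex without a condom | sex (2.2.4, 8.5.1, 9.1) |
| SMS unit | times per week | days per week, 0 to 7 |
| Calendar | contacts with condom use, past 3 months | days with sex and days with dPEP, days -14 to -3 |

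The coverage row is inconsistent with the dosing row within the SAP itself. For the calendar, that holds whatever SMS question was sent.

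**2. Expected coverage on simple day counting**

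Let c be the condom-protected share of sex days (assumed). The woman doses after every condomless act and never after a protected one.

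- All-sex denominator: coverage = (sex days − protected days) / sex days = 1 − c.
- Condomless denominator: coverage = 100%.

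Example with c = 30% and 10 sex days: (10 − 3)/10 = 70% against 7/7 = 100%. Expected coverage reaches the 80% cut when 1 − c = 0.80, that is c = 20%.

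**3. Effect of the 72-hour wording**

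A dose taken for a later condomless act may fall within 72 hours of an earlier protected day and credit it. A simulation covered both readings, with 40,000 women per setting. Its assumptions were:

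- a 12-day window (day -14 to day -3);
- 1 to 3 sex days per week on average, independent from day to day;
- same-day dosing after condomless sex;
- doses in the 3 days after the window visible for crediting;
- women with no sex in the window excluded.

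Ranges run over 1 to 3 sex days per week.

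| c | Simple count: mean coverage | Simple count: share below 80% | 72 h credit: mean coverage | 72 h credit: share below 80% |
|---|---|---|---|---|
| 0% | 100% | 0% | 100% | 0% |
| 10% | 90% | 18–21% | 93–98% | 5–12% |
| 20% | 80% | 34–42% | 86–94% | 12–24% |
| 30% | 70% | 48–62% | 78–90% | 22–36% |
| 50% | 50% | 70–88% | 60–76% | 47–59% |

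With a condomless denominator the share below 80% is 0% throughout. Some women fall short even at c = 10% because a 12-day window holds few sex days: 12 × 2/7 = 3.4 at two per week. With four sex days, one uncovered day gives 3/4 = 75%; with five it gives 4/5 = 80%. These shares are per window. Pooling over visits would reduce this coarseness.

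**4. The SMS item: two cases**

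- *Condomless sex was asked.* SAP 9.1 then reports condomless-sex frequency under the label of sexual frequency. A drop in condom use with unchanged sexual frequency would look like more sex. The SMS coverage denominator is then already the right construct.
- *Any sex was asked.* SAP 9.1 is then labelled correctly. SMS coverage includes condom-protected days, and nothing in the reply allows them to be removed.

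In either case the weekly SMS totals carry no timing within the week, so they cannot by themselves apply the 72-hour criterion.

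**The case against.** **The SAP may simply describe the question as sent.** The protocol offers its SMS text only as an example. The SAP's three descriptions agree with each other, a 0 to 7 range fits a question about days, and the latest SAP version was issued as a clarification near the end of data collection. This is a fair reading and may be the likelier one. It does not settle the point, because neither document acknowledges the change of construct and unit, and the calendar rule is untouched by it.

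**A reader might infer that the mismatch both mislabels 9.1 and corrupts SMS coverage.** The documents do not support that. As the two cases show, each consequence needs a different wording to have been sent.

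**A reader might also infer that any woman with condoms on more than 20% of sex days must fail the 80% cut.** That ignores the 72-hour wording. With crediting, 22–36% of perfectly instructed women fall below 80% at c = 30%, so most pass.

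**Little inference depends on the coverage rule.** This stands. The coverage tables are descriptive. The adherence-effectiveness analysis in 8.5.2 uses doxycycline detection in hair, and the per-protocol analysis in 7.5.3 uses documented discontinuation. Condom use is also compared by arm in 9.1.1, although that item is quarterly, concerns last sex only, and pools no sex with condom use.

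**The calendar may not hold condom use by day.** The protocol says that it records contacts with condom use, but the SAP measure lists only days with sex and days with dPEP. A day-level field is a reasonable expectation that should be confirmed.

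**Conclusion.** The point holds in two parts. First, the SAP 8.5.1 denominator contradicts the SAP's own dosing instruction and the protocol's adherence definition, and it understates calendar coverage for women who use condoms. The expected shortfall is about c on simple day counting and smaller with 72-hour crediting. At assumed c of 10% to 50%, between 5% and 88% of perfectly instructed women would score below 80% in a visit window, depending on c, sexual frequency and the crediting rule. The documents give no condom-use rate, so these figures illustrate the mechanism and do not predict the result. At c = 0 there is no error.

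Second, the SMS item has two incompatible definitions. The documents do not show which question was sent, so they do not establish that 9.1 is mislabelled.

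The impact is confined to secondary adherence and behaviour results. The primary endpoint and its analysis are unaffected. The correction is worth making because the rule is wrong as written and cheap to put right.

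**What to change.** 1. **SAP 8.5.1, calendar.** Define the denominator as days with condomless sex, using the condom-use data from the timeline follow-back calendar. State how a dose within 72 hours is credited to more than one day. Report the all-sex version only as a supplement.
2. **SMS item (SAP 2.2.4, 8.5.1, 9.1).** Give the question as sent, including whether it asked for times or days.
   - If it was condomless sex, retitle and interpret 9.1 as condomless-sex frequency.
   - If it was any sex, keep 9.1 and note beside the SMS coverage table that it includes condom-protected days and cannot be filtered.
   - In both cases, say that the weekly counts do not apply the 72-hour criterion.

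The cost is SAP wording and one filter on data that the protocol already collects, provided condom use is held by day in the calendar. No new data collection is needed. The SAP's introduction allows revision until database lock.

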#### **9.1.1 Changes in sexual risk behavior**

Survey data collected quarterly, asking: "Was a condom used at last sex (N/Y)?" We will compare no sex/used condom at last sex over time to investigate whether they differ by arm using GEE with Poisson distribution.

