## Rationale

### *Rationale for a randomized trial*

We posit that there is equipoise to conduct a randomized evaluation at this time: while dPEP has demonstrated efficacy in one trial, it was relatively small in size and limited to MSM in France. Data specific to women are needed to know if dPEP is effective and safe. Additionally, the potential disadvantages of dPEP, such as

antibiotic resistance, tolerability, and low adherence, have not been studied in women and justify the use of a control arm. Randomization in 1:1 allocation will be the most efficient for evaluating efficacy of dPEP and balancing unknown acceptability. Like IPERGAY, we propose that an open-label design allows for optimal evaluation of effectiveness. First, the open-label model directly addresses questions about acceptability, as participants will react to dPEP itself, not a blinded, potentially placebo version. Second, an open-label design is likely to result in greater (and more realistic) adherence – in placebo-controlled trials of PrEP among African women, adherence was very low, and subsequent qualitative studies found concerns about receiving a placebo as a principal reason, with greater adherence in recent open-label studies. Third, the design will directly allow assessment of sexual behavior changes (i.e., disinhibition) related to STI PEP, which could overwhelm dPEP's benefits and is only assessable if subjects know if they are actually taking active dPEP.

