## 6.0 STUDY PROCEDURES

	Study Visit Month	S	0	3	6	9	12
Study coordination							
Obtain informed consent Screen for inclusion/exclusion Randomization Collect updated contact information Reimbursement	Obtain informed consent	X					
	Screen for inclusion/exclusion	X	X				
	Randomization		X				
	Collect updated contact information	X	X	X	X	X	X
	Reimbursement	X	X	X	X	X	X
Questionnaires							
Demographic information Behavioral questionnaire HIV risk perception Social Harms and IPV Sexual behavior and exposure history PrEP adherence dPEP adherence (timeline follow-back calendar) Fertility intention Quality of Life	Demographic information	X	X				
	Behavioral questionnaire		X		X		X
	HIV risk perception	X	X	X	X	X	X
	Social Harms and IPV	X	X	X	X	X	X
	Sexual behavior and exposure history	X	X	X	X	X	X
	PrEP adherence	X	X	X	X	X	X
	dPEP adherence (timeline follow-back calendar)			X a	X a	X a	X a
	Fertility intention	X	X	X	X	X	X
	Quality of Life	X	X	X	X	X	X
Clinical Study Care							
Medication review General symptom assessment WHO pregnancy checklist STI symptom assessment Supply condoms Contraception counseling and provision/referral Risk reduction counseling dPEP pill count and refill	Medication review	X	X	X	X	X	X
	General symptom assessment		X	X	X	X	X
	WHO pregnancy checklist	X		X	X	X	X
	STI symptom assessment	X	X	X	X	X	X
	Supply condoms	X	X	X	X	X	X
	Contraception counseling and provision/referral	X	X	X	X	X	X
	Risk reduction counseling	X	X	X	X	X	X
	dPEP pill count and refill			X a	X a	X a	X a
Sample collection							
HIV testing (rapid test) Urine pregnancy testing (rapid test) Syphilis testing (serum RPR) Creatinine (serum) CT/NG testing and resistance (endocervical swabs) c Hair PrEP and doxycycline drug levels Trichomonas screening (vaginal swab)	HIV testing (rapid test)	X		X	X	X	X
	Urine pregnancy testing (rapid test)	X b	X	X b	X b	X b	X b
	Syphilis testing (serum RPR)		X	X	X	X	X
	Creatinine (serum)	X b					
	CT/NG testing and resistance (endocervical swabs) c	X	X	X	X	X	X
	Hair PrEP and doxycycline drug levels		X	X	X	X	X
	Trichomonas screening (vaginal swab)		X	X	X	X	X
Archive							

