### **Instructions for evaluations**

#### *Questionnaires and Interviews:*

**Quantitative data:** Demographic and behavioral surveys will be administered at each visit, using questions we have used extensively in our prior trials (**Table 4**). All participants will complete questionnaires each study visit on facilitators and barriers to STI prevention and dPEP.

Table 4. Data collection on facilitators of and barriers to STI prevention and dPEP: all have been used in our prior work (Table 5)	
Structural	E=enrollment, Q=quarterly, 6=Month 6 visit, 12=Month 12 visit
Socioeconomic status	employment (E), income (E), presence of running water/electricity/metal roof/TV/phone at home (WAMI) (E)
Individual	
Demographic factors	age (E), race/ethnicity/tribe (E), educational level (E), time spent traveling for clinic visit (E, 6, 12)
Alcohol use	# days in last week consumed, rapid alcohol problems screen-quantity frequency (RAPS4-QF) (E, 6, 12)
Depression	somatization, obsessive-compulsive, interpersonal sensitivity, anxiety and depression (HSCL-D) (E, 6, 12)
HIV risk perception	what do you think is your risk of getting (giving) HIV and STIs from (to) your partner? (4 item Likert scale) (E, Q)
Prevention strategies	perceived dPEP efficacy for STI prevention, perceived PrEP efficacy for HIV prevention (E, Q)
Social Harms	physical, social and economic social harms (E, Q)
Dyadic	
Relationship	partnership status (E, Q), social support (Modified UNC-Duke) (E, 6, 12), partner violence (E, Q)
Sexual behavior	sex frequency (E, Q), condom use (E, Q), sexual power (E, 6, 12)
Fertility intention	# of children (E), current pregnancy (E, Q), goal # of children and fertility intentions (E, Q)
HIV stigma	scale plus disclosure (e.g., serodiscordant status) to family/friends/religious leaders & adverse effects (E, 6, 12)

**Sexual behavior questionnaire:** Participants will be asked to complete a sexual behavior questionnaire using timeline follow-back calendar to record number and type of sexual contacts (including condom use) in the past 3 months at each study visit.

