### **6.5. Demographic and Baseline Characteristics**

#### **6.5.1. Demographics and risk characteristics**

The following baseline demographics and risk characteristics will be presented separately by arm for the ITT cohort.

- Age in years
- Education
- Sexual risk (i.e. number of partners, transactional sex, condom use with last sex)
- Living situation
- Preferred language
- Marital status
- Number of live births
- Earns her own income (Y/N)

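### SAP 9.1.1 specifies no adjustment for a woman's own condom use at enrolment, so its test for risk compensation may give up precision that data already collected could recover

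*SAP*

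**What the plan says.** **The models.** SAP 9.1.1 analyses a quarterly binary item: "We will compare no sex/used condom at last sex over time to investigate whether they differ by arm using GEE with Poisson distribution". SAP 9.1 treats sexual frequency in the same way: "We will compare frequency of sexual activity over time to investigate whether they differ by arm using a GEE with Poisson distribution". Its data come from a different source: "SMS surveys collected weekly ask all participants how many days of the last week they had sexual intercourse with responses ranging from 0-7". Neither section lists covariates, says whether the enrolment record is an outcome row, or says whether the arm effect is an average over follow-up or an arm-by-time term.

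**The enrolment data.** Protocol Table 4 lists, for enrolment (E) and each quarter (Q), "sex frequency (E, Q), condom use (E, Q), sexual power (E, 6, 12". The schedule in Protocol section 6.0 marks the row "Sexual behavior and exposure history" at screening, Month 0 and every quarterly visit. SAP 6.5.1 includes among the baseline characteristics "Sexual risk (i.e. number of partners, transactional sex, condom use with last sex".

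**Why behaviour matters.** The protocol's rationale for a randomised trial gives, as its third reason for an open-label design, the assessment of "sexual behavior changes (i.e., disinhibition) related to STI PEP, which could overwhelm dPEP's benefits".

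**Adjustment elsewhere.** Protocol section 10 says only that behaviour will be compared between arms by repeated measures. Its adjusted analyses are optional and sit under the primary STI analysis. SAP 7.5.3 allows for baseline sexual risk, but in the per-protocol STI model. Nothing supplies a baseline covariate for the behaviour outcomes.

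**The concern.** Whether a woman used a condom, or had no sex, before randomisation is the natural predictor of the same item afterwards. A model that leaves it out counts stable differences between women as noise in the arm comparison. The item is on file and will be tabulated at baseline, so using it as a covariate needs no new data.

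The stake is the width of the confidence interval around a harm estimate. For an efficacy outcome, low precision counts against the intervention. For a harm outcome, it makes a null result more likely whether or not behaviour has changed. The plan gives no power calculation for behaviour, so a reader has no stated measure of how large a change the trial could miss.

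**Working it through.** **1. The plan's own figure.** The only power statement concerns STI incidence (SAP 3.3.1). For a hazard ratio of 0.5, 80% power and two-sided alpha 0.05, events = 4 × (1.960 + 0.842)² / (ln 0.5)² = 65.3, so 66. Women = 66 / ((0.22 + 0.11)/2) = 400, and 400 / 0.90 = 444.4, so 445 against the stated 446. The figure reproduces. It says nothing about power for behaviour.

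**2. Inputs for the behaviour outcome.**
- From the documents: four follow-up visits (Months 3, 6, 9 and 12), 223 women per arm and 10% loss (about 200 per arm), and two-sided alpha 0.05 (SAP 7.1). The protocol states 550 women; the SAP's 446 is used here. The variance ratios below do not depend on it.
- Assumed, because the documents give none: equal correlation rho between any two visits including enrolment, the prevalence of the outcome, and the arm difference.

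**3. Variance of the arm effect**, in units of the one-visit variance:
- follow-up mean, unadjusted: (1 + 3·rho)/4
- adjusted for the enrolment value: (1 + 3·rho)/4 − rho²
- proportional cut: rho² / ((1 + 3·rho)/4)

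**4. Power from an 80% unadjusted start:** Φ((1.960 + 0.842)/√ratio − 1.960), where ratio = adjusted / unadjusted variance.

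| rho | Unadjusted | Adjusted | Ratio | Variance cut | Power |
|---|---|---|---|---|---|
| 0.1 | 0.325 | 0.315 | 0.969 | 3% | 81% |
| 0.2 | 0.400 | 0.360 | 0.900 | 10% | 84% |
| 0.3 | 0.475 | 0.385 | 0.811 | 19% | 88% |
| 0.5 | 0.625 | 0.375 | 0.600 | 40% | 95% |

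At rho 0.2 the cut is worth an unadjusted trial of 446/0.900 = 496 women; at rho 0.5, 446/0.600 = 743.

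**5. An absolute example.** Take 200 women per arm, 40% with no sex or condom at last sex, and a 10-point arm difference. At rho 0.5 the unadjusted SE is √(2 × 0.24 × 0.625/200) = 0.0387 and the adjusted SE is √(2 × 0.24 × 0.375/200) = 0.0300, so power goes from 73% to 91%. At rho 0.3 it goes from 84% to 91%, and at rho 0.2 from 90% to 92%. For an 8-point difference the three pairs are 54% to 76%, 66% to 75% and 73% to 78%.

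**6. Check by simulation.** The formula treats the outcome as linear. A simulation used a binary outcome and a modified Poisson GEE with independence working correlation, robust standard errors and visit indicators (402 women, four follow-up visits, assumed 50% against 41%, 1,000 runs per scenario). The last column keeps Month 0 as a row and tests an arm-by-post term.

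| Correlation with enrolment | Unadjusted | Adjusted | Arm-by-post |
|---|---|---|---|
| 0.19 | 84% | 86% | 49% |
| 0.33 | 74% | 82% | 58% |
| 0.49 | 62% | 83% | 68% |

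Results were similar at 30% against 22% and 70% against 61%. With no true difference, the rejection rate was 5.8% unadjusted and 5.3% adjusted.

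**7. Scope.** These figures are for a binary quarterly item and an average follow-up difference. They do not carry over to the weekly counts in SAP 9.1, and a pure arm-by-time slope over follow-up visits would gain little from a baseline main effect.

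**The case against.** The strongest reply is that this is silence in a brief description of an additional secondary analysis. Where the SAP means arm alone it says so, as in the primary model (SAP 7.5.1), so the omission in 9.1.1 is not a decision against adjustment. An unadjusted behaviour model would also match that primary model. The behaviour outcomes have no power target or decision rule. The intention-to-treat STI comparison already captures the net effect of any disinhibition, and vaginal swabs are archived for possible Y-chromosome testing as an objective marker. All of this stands and limits the weight of the point. It does not remove the gain from naming the covariate in advance.

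Four stronger readings are tempting, and the documents do not support them:
- **The SAP rejects adjustment.** It only fails to specify it.
- **The estimate is diluted by about a fifth.** This holds only if Month 0 is kept as one of five outcome rows under a single arm main effect, a model the SAP does not describe. With an arm-by-post term the enrolment row serves as the reference, and the lower power comes from added variance.
- **The same power loss applies to SAP 9.1.** Its outcome is an opt-in weekly SMS count with no pre-randomisation SMS survey described. The available covariate is from a different instrument, with unknown correlation.
- **A null result will be reported as no risk compensation.** No section says so.

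**Conclusion.** The point holds for SAP 9.1.1 as a minor, no-cost gain in precision. Validity is not in question: the unadjusted follow-up comparison is protected by randomisation.

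The size depends on a correlation that the documents do not give. The gain is negligible near rho 0.1, small at 0.2 and material from about 0.3. It also rests on equal correlation between visits and on an arm effect averaged over follow-up. For SAP 9.1 the direction is plausible, but no size can be stated.

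**What to change.** In SAP 9.1.1, state that:
- the outcome rows are Months 3, 6, 9 and 12;
- the covariates are arm, visit and the enrolment value of the same item (no sex, or condom at last sex), using the latest value recorded before randomisation;
- standard errors are robust, and the adjusted risk ratio is reported with its 95% CI;
- the unadjusted estimate is reported as sensitivity;
- an arm-by-visit term is kept as a further analysis if diverging trajectories are of interest, so that the covariate does not replace a comparison the plan intends;
- women with a missing enrolment item are kept by a missing indicator.

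In SAP 9.1, enrolment sex frequency from the questionnaire may be added as a covariate, with no claim about the gain.

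The cost is a short addition to each section and no new data. SAP section 1 allows revision until the final version is filed before database lock.
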